1 SYNOPSIS

Protocol Title: Safety Study of Nivolumab for Selected Advanced Malignancies in India

Study Phase: Phase 4

[REDACTED]

[REDACTED]

[REDACTED]

[REDACTED]

Study Population:

The study population includes:

- adult patients with locally advanced or metastatic NSCLC after prior chemotherapy
- adult patients with advanced RCC after prior therapy.

Objectives and Endpoints:

Objective	Endpoint
Primary	

• To assess the safety and tolerability of nivolumab for the treatment of locally advanced or metastatic NSCLC after prior chemotherapy or advanced RCC after prior therapy	
• Incidence and severity of treatment related adverse events (AEs)

Objective	Endpoint
Secondary	

 • To estimate the incidence and severity of treatment-related select AEs in all treated participants. • To estimate the incidence of all treatment-related serious adverse events (SAEs) • To estimate the incidence of AEs that lead to discontinuation of treatment with nivolumab. 	
 • Incidence and severity of treatment-related select AEs, as specified in Section 10.3.2 in all treated participants • Incidence of all treatment-related SAEs • Incidence of AEs that lead to discontinuation from treatment with nivolumab

Overall Design:

This is a Phase 4, open-label, single arm, multi-center, prospective safety study to be conducted in India with participants with either locally advanced or metastatic NSCLC (Stage IIIb/IV NSCLC) with squamous histology or non-squamous histology who have progressed during or after at least 1 prior chemotherapy (N= 70) or advanced RCC who have progressed during or after at least 1 prior therapy (N= 30). Potential participants will undergo screening evaluations to determine eligibility within 28 days prior to first dose. Participants who meet the protocol-defined inclusion/exclusion criteria will be prospectively enrolled in a sequential manner. All enrolled participants will be treated with nivolumab administered intravenously over 60 minutes at 3 mg/kg every 2 weeks. Each 14 day dosing period will constitute a cycle. Treatment will continue as long as clinical benefit is observed for a maximum of 24 weeks or until treatment is no longer tolerated by the participant or withdrawal of consent. The treatment period for this study is 26 weeks, which corresponds to 24 weeks of treatment and 2 weeks of follow-up after the final on-study dose of nivolumab. Participants who are observed to continue to receive clinical benefit from nivolumab at 26 weeks will continue treatment via commercial supply (provided by BMS) as long as clinical benefit is observed or until treatment is no longer tolerated by the participant. Any participant who discontinues treatment with nivolumab before 24 weeks on study will be followed for 100 days after discontinuation of study drug or for a total of 26 weeks from first on-study treatment with nivolumab, whichever is earliest.

Safety will be evaluated throughout the treatment period and during the follow up of participants who discontinue treatment before 24 weeks by physical exams including vital signs, AE/SAE monitoring, laboratory evaluations and recording of concomitant medications.

Data analyses will be conducted only on the safety data collected within the maximum of the 26 week study period, which will include safety collected during the follow-up of participants who discontinue treatment before 24 weeks.

All SAEs after 26 weeks of study duration for patients on commercial nivolumab supply will be reported to India Health Authority as part of spontaneous reporting.

[figure not shown]
Number of Participants:

A total of 100 participants will be enrolled: 70 NSCLC and 30 RCC

Treatment Arms and Duration: All participants will be treated with nivolumab 3mg/kg IV q 2 weeks on Day 1 of each cycle. Each treatment cycle is 14 days long. The treatment period for all participants is a maximum of 26 weeks. Participants who are observed to continue to receive clinical benefit from treatment with nivolumab at 26 weeks may continue treatment via commercial supply (provided by BMS) as long as clinical benefit is observed or until treatment is no longer tolerated by the participant.

Study treatment:

Study Drug for CA209887		
Medication	Potency	IP/Non-IP
Nivolumab	10 mg/mL concentrate for solution for infusion	IP

2 SCHEDULE OF ACTIVITIES

Table 2-1: CA209887 Screening procedures and assessments

Procedure	Screening Visit	Notes
		Screening visit will occur within 28 days before start of nivolumab
Eligibility Assessments		
Informed Consent	X	
IVRS	X	An Interactive voice recognition system (IVRS) will be used to assign participant numbers.
Inclusion/Exclusion Criteria	X	
Medical History	X	Medical history will include smoking history, and comorbidities. Mutation status of EGFR and ALK will be collected if available. Additional biopsies for mutation status, if not previously tested, are not required.
Safety Assessments		
Physical Examination	X	Includes height, weight, and ECOG PS (Appendix 1). Full physical exam required at baseline.
Vital Signs	X	Temperature, BP, HR, RR. Obtain vital signs at screening visit and within 72 hours of first dose
Assessment of Signs and Symptoms	X	After obtaining Informed Consent, assess all signs and symptoms within 14 days of first dose, prior to study treatment initiation
Concomitant medications	X	Within 14 days of first dose
Laboratory Tests	X	Laboratory Tests performed locally within 14 days prior to first dose (unless otherwise specified): CBC with differential, serum chemistry (BUN or serum urea level, serum creatinine, sodium, potassium, calcium, magnesium, phosphate, chloride, and glucose), liver function tests (AST, ALT, total bilirubin, alkaline phosphatase, albumin, LDH). TSH, free T3, free T4 (within 28 days prior to first dose), hepatitis B surface antigen (HBsAg) and hepatitis C antibody (HCV Ab) or HCV RNA.
Pregnancy Test	X	Within 24 hours prior to first dose for WOCBP only (serum or urine at the site).

ALT = alanine aminotransferase, AST = aspartate aminotransferase; BP = blood pressure; BUN = blood urea nitrogen; CBC = complete blood count; ECOG = Eastern Cooperative Oncology Group; HR = heart rate; LDH = lactate dehydrogenase; NCI CTCAE = National Cancer Institute Common Terminology Criteria for AEs; RR = respiratory rate, TSH = thyroid stimulating hormone, T3 = triiodothyronine, T4 = thyroxine; WOCBP = Women of Childbearing Potential

Table 2-2: CA209887: On-Study Procedures and assessments

Procedure	Each Cycle (Every 2 weeks)	Notes
Safety Assessments		
Physical Measurements (including Performance Status)	X	Collect weight and ECOG Performance Status (Appendix 1) within 72 hours prior to dosing. Targeted physical examination may be performed if clinically indicated and is recommended to include cardiovascular, gastrointestinal, pulmonary and neurological exam for participants with brain metastases.
Vital Signs	X	Within 72 hours prior to dosing, tests includes temperature, BP, HR and RR
Serious Adverse Event Assessment	X	Assessed using NCI CTCAE v 4.0 (continuously monitored throughout treatment period)
Adverse Events Assessment	X	Assessed using NCI CTCAE v 4.0(continuously monitored throughout treatment period)
Review Concomitant Medication	X	
Laboratory Tests	X ^{a, b, c, d}	CBCs with differential ^a Serum chemistry tests ^b and liver function tests ^c should be checked every cycle, and the results should be obtained prior to dosing. Thyroid Function Test (TFTs) ^d should be checked every 6 weeks.
Pregnancy Test	Every 4 weeks	Completed more frequently if required by local standards (serum or urine as required by standard of care at the site).
Clinical Drug Supplies		
Administration of nivolumab (3 mg/kg)	X	All enrolled participants continue treatment every 2 Weeks. Treatment should be continued as long as clinical benefit is observed for a maximum of 24 weeks or until treatment is no longer tolerated by the participant or withdrawal of consent. Record Study Drug Infusion start and stop

BP = blood pressure; CBC = complete blood count; ECOG = Eastern Cooperative Oncology Group; HR = heart rate; LDH = lactate dehydrogenase; NCI CTCAE = National Cancer Institute Common Terminology Criteria for AEs; RR = respiratory rate.

[figure not shown]
^a CBCs with differential includes white blood cell count, lymphocyte count, absolute neutrophil count, hemoglobin, hematocrit, and platelet count. Results to be obtained prior to dosing on infusion days.

^b Serum chemistry tests include blood urea nitrogen (BUN) or serum urea level, serum creatinine, sodium, potassium, calcium, magnesium, phosphate, chloride, and glucose.

^c Liver function tests include AST, ALT, total bilirubin, alkaline phosphatase, albumin, LDH.

^d Thyroid function testing including TSH (reflex to free T3 and free T4 if abnormal result).

Table 2-3: CA209887: Follow-up Procedures

Procedure	Follow-up phase	Notes
	
Follow-up Visit 1: 30 days (+/- 5 days) after last dose or on the date of discontinuation (+/- 5 days) if date of discontinuation is greater than 35 days after last dose.
 
Follow up Visit 2: 70 days (+/- 5 days) after Follow up Visit 1.
	
Participants who discontinue on-study treatment with nivolumab before 24 weeks will be followed for 100 days after the last on-study dose of nivolumab or for a maximum of 26 weeks from the date of the first on-study dose of nivolumab, whichever occurs earliest.

Safety Assessments		
Physical measurements	X	
Vital Signs	X	Temperature, BP, HR and RR
Adverse Events Assessment	X	
Serious Adverse Event Assessment	X	All SAEs after 26 weeks of study duration for participants on commercial nivolumab supply will be reported to India Health Authority as part of spontaneous reporting.
Review Concomitant Medication	X	
Laboratory Tests	X	Laboratory tests as listed for on treatment assessment in Table 2-2 .
Pregnancy Test	X	Completed more frequently if required by local regulations (serum or blood as required by standard of care at the site).

BP = blood pressure; ECOG = Eastern Cooperative Oncology Group; HR = heart rate; RR = respiratory rate.

[Redacted text block]

[Redacted text block]

[Redacted text block]

[Redacted text block]

[Redacted text block]

[Redacted text block]

[Redacted text block]

[Redacted text block]

[Redacted text block]

[Redacted text block]

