5 STUDY DESIGN

5.1 Overall Design

This is a Phase 4, open-label, single arm, multi-center, prospective safety study to be conducted in India with participants with either locally advanced or metastatic NSCLC (Stage IIIb/IV NSCLC) with squamous histology or non-squamous histology who have progressed during or

after at least 1 prior chemotherapy (N= 70) or advanced RCC who have progressed during or after at least 1 prior therapy (N= 30). Potential participants will undergo screening evaluations to determine eligibility within 28 days prior to first dose. Participants who meet the protocol defined inclusion/exclusion criteria will be prospectively enrolled in a sequential manner. All enrolled participants will be treated with nivolumab administered intravenously over 60 minutes at 3 mg/kg every 2 weeks. Each 14 day dosing period will constitute a cycle. Treatment will continue as long as clinical benefit is observed for a maximum of 24 weeks or until treatment is no longer tolerated by the participant or withdrawal of consent. The treatment period for this study is 26 weeks, which corresponds to 24 weeks of treatment and 2 weeks of follow-up after the final on-study dose of nivolumab. Participants who are observed to continue to receive clinical benefit from nivolumab at 26 weeks will continue treatment via commercial supply (provided by BMS) as long as clinical benefit is observed or until treatment is no longer tolerated by the participant. Any participant who discontinues treatment with nivolumab before 24 weeks on study will be followed for 100 days after discontinuation of study drug or for a total of 26 weeks from first on-study treatment with nivolumab, whichever is earliest.

[figure not shown]
Safety will be evaluated throughout the treatment period and during the follow up of participants who discontinue treatment before 24 weeks by physical exams including vital signs, AE/SAE monitoring, laboratory evaluations and recording of concomitant medications.

Data analyses will be conducted only on the safety data collected within the maximum of the 26 week study period, which will include safety collected during the follow-up of participants who discontinue treatment before 24 weeks.

All SAEs after 26 weeks of study duration for participants on commercial nivolumab supply will be reported to India Health Authority as part of spontaneous reporting.

The study design schematic is presented in [Figure 5.1-1](#).

Figure 5.1-1: Study Design Schematic

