9.2.1 Time Period and Frequency for Collecting AE and SAE Information

The collection of nonserious AE information should begin at initiation of study treatment until the follow-up contact, at the time points specified in the Schedule of Activities ([Section 2](#)). Nonserious AE information should also be collected from the start of a placebo lead-in period or other observational period intended to establish a baseline status for the participants.

Sections 5.6.1 and 5.6.2 in the Investigator Brochure (IB) represent the Reference Safety Information to determine expectedness of serious adverse events for expedited reporting. Following the participant's written consent to participate in the study, all SAEs, whether related or not related to study drug, must be collected, including those thought to be associated with protocol-specified procedures.

All SAEs must be collected that occur during the screening period, during treatment, and within 100 days or a maximum of 26 weeks of discontinuation of dosing, whichever is earliest. If applicable, SAEs must be collected that relate to any later protocol-specified procedure (e.g., a follow-up skin biopsy).

The investigator must report any SAE that occurs after these time periods and that is believed to be related to study drug or protocol-specified procedure.

- Medical occurrences that begin before the start of study treatment but after obtaining informed consent will be recorded on the appropriate section of the eCRF section.
- All SAEs will be recorded and reported to Sponsor or designee within 24 hours, as indicated in [Appendix 6](#).
- The investigator will submit any updated SAE data to the sponsor within 24 hours of this being available.

Investigators are not obligated to actively seek AEs or SAEs in former study participants. However, if the investigator learns of any SAE, including a death, at any time after a participant has been discharged from the study, and he/she considers the event reasonably related to the study treatment or study participation, the investigator must promptly notify the sponsor.

The method of evaluating, and assessing causality of AEs and SAEs and the procedures for completing and reporting/transmitting SAE reports are provided in [Appendix 6](#).

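### Follow-up Visit 2 is not reconciled with the 26-week cap: for last doses 8 to 11 it cannot fall inside the analysis window, and no week-26 assessment takes its place

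*Protocol*

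**What the plan says.** The visit column of Protocol Table 2-3 gives "Follow-up Visit 1: 30 days (+/- 5 days) after last dose". Visit 1 moves to the discontinuation date "if date of discontinuation is greater than 35 days after last dose". The second visit is then defined only by reference to the first: "Follow up Visit 2: 70 days (+/- 5 days) after Follow up Visit 1".

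The note column of the same table sets a different end point. It covers those who stop before week 24 and gives two limits. One is 100 days from their final dose; the other reads: "or for a maximum of 26 weeks from the date of the first on-study dose of nivolumab, whichever occurs earliest". SAP Appendix 1 repeats both the visit rule and the cap.

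The analysis uses the cap. Protocol Sections 5.1 and 10.3.2 state: "Data analyses will be conducted only on the safety data collected within the maximum of the 26 week study period". SAP Section 6.1.2 applies the same limit to off-treatment participants. It selects AEs by when the event occurred, and laboratory and vital-sign evaluations by when they were taken.

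Protocol Section 9.2.1 ties nonserious AE collection to the schedule: "until the follow-up contact, at the time points specified in the Schedule of Activities". It defines SAE collection by period.

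For completers, Protocol Section 5.1 describes a 26-week treatment period made up of 24 weeks of treatment and 2 weeks of follow-up. Table 2-2 places AE and SAE assessment under continuous monitoring for that period, but its visits and laboratory tests are per cycle, before dosing. Section 9.4 confines the follow-up assessments to participants who stop before 24 weeks. The text of neither document names a week-26 or end-of-study visit. The schematic in Figure 5.1-1 was not available for this check.

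**The concern.** The two columns of Table 2-3 agree only for participants who stop early enough for 100 days after the last dose to come before week 26. For later stoppers the cap closes follow-up at week 26, while the visit rule places the last visit beyond it. A site following the table cannot tell whether that visit is held, moved forward or dropped.

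The primary endpoint is the incidence and severity of treatment-related AEs. The select AEs among the secondary endpoints include hepatotoxicity with asymptomatic liver-test elevations, renal toxicity and endocrinopathies. Events of this kind may come to light only through a blood test. If no test is scheduled in the last weeks of the window, they are not found. Missed events can only lower the observed incidence. Because the length of the gap depends on when treatment stopped, ascertainment also differs between participants.

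**Working it through.** **Inputs.** First dose on day 0, and dose k on day 14(k − 1) with no delays (14-day cycles, Protocol Section 5.1). Visit 1 = last dose + 30, range +25 to +35. Visit 2 = Visit 1 + 70 (±5), so last dose + 100, range +90 to +110 when both tolerances are used (Table 2-3). Window end = the smaller of last dose + 100 and day 182.

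**The plan's own figures.** 30 + 70 = 100 days, which matches the 100-day limit. (24 + 2) × 7 = 182 days, which matches 26 weeks. Both reproduce, so the rule and the cap agree until the 26-week limit becomes the earlier one.

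**When Visit 2 leaves the window.** Nominally: last dose + 100 > 182, so a last dose after day 182 − 100 = 82. With both tolerances used early: last dose + 90 > 182, so a last dose after day 182 − 90 = 92.

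**By last dose.** Uncovered days = window end minus the latest visit that falls inside the window. *At best* uses the tolerances to the participant's advantage.

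| Last dose | Day | Visit 1 (range) | Visit 2 (range) | Window end | Uncovered, nominal | Uncovered, at best |
|---|---|---|---|---|---|---|
| 6 | 70 | 100 (95–105) | 170 (160–180) | 170 | 0 | 0 |
| 7 | 84 | 114 (109–119) | 184 (174–194) | 182 | 68 | 0 |
| 8 | 98 | 128 (123–133) | 198 (188–208) | 182 | 54 | 49 |
| 9 | 112 | 142 (137–147) | 212 (202–222) | 182 | 40 | 35 |
| 10 | 126 | 156 (151–161) | 226 (216–236) | 182 | 26 | 21 |
| 11 | 140 | 170 (165–175) | 240 (230–250) | 182 | 12 | 7 |
| 12 | 154 | 184 (179–189) | 254 (244–264) | 182 | 28 | 0 |

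Example, dose 8: 182 − 128 = 54 nominally; 182 − 133 = 49 if Visit 1 is as late as allowed. Doses 1 to 5 behave like dose 6.

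Doses 7 and 12 are borderline. Each nominal visit (Visit 2 for dose 7, Visit 1 for dose 12) is on day 184, 2 days late, and its tolerance reaches back inside the window. Doses 8 to 11 are not borderline: no permitted timing brings Visit 2 inside.

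**Dosing delays.** The first last-dose number for which Visit 2 is out of reach even with tolerance is 9 at 12-day spacing (the protocol minimum), 8 at 14 days, 7 at 17 days and 6 at 21 days. The 17- and 21-day spacings are assumed, for illustration. The day-92 rule does not depend on spacing.

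**Late discontinuation date.** The table uses the last-dose anchor. If discontinuation is 36 days after the last dose, Visit 1 is on day 36 and Visit 2 on day 36 + 70 = 106 after the last dose (range 96 to 116). A later Visit 1 shortens the gap after it, but pushes Visit 2 further out.

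**Completers.** If the final dose is on day 168, the last scheduled assessment is the pre-dose visit, and 182 − 168 = 14 days follow with none. If 24 weeks means 12 doses, the last is on day 154, and Visit 1 (days 179–189) would cover week 26 only if Table 2-3 is read as applying to completers.

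**The case against.** The strongest reply is that a late visit still looks back. SAP Section 6.1.2 admits AEs by onset, so a Visit 2 on day 198 could record an event that began by day 182, and no text cancels such a visit. This stands for AEs, but only if the visit is held beyond the stated end of follow-up. Section 9.2.1 does not oblige investigators to seek events in former participants, and the Section 5.1 limit to data collected within 26 weeks pulls the other way. It does not help laboratory results, which SAP Section 6.1.2 drops when they are dated after the window. The same look-back answers a worry about late discontinuation: a Visit 2 after the 100-day limit can still cover the AE window before it.

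A reader might go further and infer that every stopper from dose 7 on, and every completer, goes unobserved at the end of the window. The documents do not support that. The 68- and 28-day figures for doses 7 and 12 disappear within the visit tolerances. Completers' AEs are under continuous monitoring for a treatment period that includes their last 2 weeks, and clinical benefit is judged at 26 weeks, which implies some contact. A 14-day tail is also no longer than an ordinary cycle. What completers lack is a named assessment and a blood test.

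A reader might also take uncovered days as missed events. SAEs are collected by period. Summaries count worst grade, so a late event matters only if it is new for that participant or of higher grade. The study tests no hypothesis. These points limit the consequence but do not reconcile the table.

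**Conclusion.** The point holds in a limited form. Table 2-3 contradicts its own cap for any last dose after day 92. With undelayed 14-day dosing and the last-dose anchor for Visit 1, that means last doses 8 to 11, with 54 down to 12 days nominally (49 down to 7 at best) and no scheduled in-window assessment. The exposure is mainly in laboratory-detected events, and in nonserious AEs if the late visit is not held. For completers the defect is an unscheduled end to the promised 2 weeks of follow-up, not an absence of AE monitoring.

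The direction of any error is towards fewer events. Its size cannot be estimated, because the documents give neither the number of participants expected to stop in this range nor event rates for those weeks. The table should be corrected, but the documents do not show that the primary result would be materially wrong.

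**What to change.** In Protocol Table 2-3 and SAP Appendix 1, replace the rule of 70 days after Visit 1 with a final follow-up visit at the earlier of 100 days after the last dose and week 26 from the first dose. Set its tolerance so that laboratory tests fall on or before that date. The present tolerances allow up to 10 days after it (100 + 5 + 5 = 110). State that the visit covers AE onsets up to the window end. This brings the uncovered days for last doses 8 to 11 to zero nominally.

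For completers, name the week-26 attendance as the point at which AEs, and laboratory tests if taken, are recorded.

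The cost is a small amendment. Visit 2 is moved rather than added, and those continuing on commercial supply can be recorded at a visit they attend anyway. The drawback is that for late stoppers the final visit comes soon after Visit 1: 12 days after it for a last dose 11 (day 182 against day 170). No dose or treatment rule changes.
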